9.7.4.2 Measurement of Treatment Compliance

Dosing compliance for a specified period is defined as the total number of IV doses actually taken by a patient during that period divided by the number of IV doses that were expected to be taken during the same period multiplied by 100. Descriptive statistics for IP compliance will be presented for each week, as well as for the whole OLTP for the Safety Population.

Dosing compliance for the background ADT during a specified period is defined as the doses actually taken by a patient during that period divided by the dose expected to be taken during the same period multiplied by 100. Descriptive statistics for ADT compliance during the OLTP will be presented for each ADT for the Safety Population.

[REDACTED]

9.7.6 Safety Analyses

The safety analysis will be performed using the Safety Population, defined as all patients who receive at least 1 dose of IP during the OLTP.

The safety parameters will include AEs; clinical laboratory, vital signs, and ECG parameters; and the BPRS+, CADSS, [REDACTED].

For each safety parameter, the last assessment made before the first dose of open-label IP will be used as the baseline for *de novo* patients, and the baseline of the first lead-in study will be used as the baseline for rollover patients for all analyses of that safety parameter. Continuous variables will be summarized by number of patients and mean, SD, median, minimum, and maximum values. Categorical variables will be summarized by number and percentage of patients.

9.7.6.1 *Adverse Events*

AEs will be coded by system organ class (SOC) and preferred term using the *Medical Dictionary for Regulatory Activities*.

For rollover patients, an AE (classified by preferred term) that occurs during the OLTP will be considered a treatment-emergent adverse event (TEAE) if it was not present before the first dose of IP in the first lead-in study or was present before the first dose of IP in the first lead-in study and increased in severity during the OLTP. If more than 1 AE is reported before the first dose of IP in the first lead-in study and coded to the same preferred term, the AE with the greatest severity will be used as the benchmark for comparison with the AEs occurring during the OLTP that were also coded to that preferred term.

For *de novo* patients, an AE (classified by preferred term) that occurs during the OLTP will be considered a TEAE if it was not present before the first dose of open-label IP or was present before the date of the first dose of open-label IP and increased in severity after the first dose of open-label IP. If more than 1 AE is reported before the first dose of open-label IP and is coded to the same preferred term, the AE with the greatest severity will be used for comparison with the AEs occurring during the OLTP that were also coded to that preferred term.

An AE that occurs more than 30 days after the date of the last dose of IP will not be considered a TEAE.

A TEAE occurring during the OLTP will be considered a newly emergent AE (NEAE) if the AE was not present before the first dose of open-label IP or was present before the first dose of open-label IP but increased in severity during the OLTP. The number and percentage of patients reporting NEAEs during the OLTP will be summarized by SOC and preferred term.

The number and percentage of patients reporting TEAEs will be tabulated by SOC and preferred term and further categorized by severity and causal relationship to the IP. If more than 1 AE is coded to the same preferred term for the same patient, the patient will be counted only once for that preferred term using the greatest severity and strictest causality for the summarization by severity and causal relationship.

The distribution of TEAEs by severity and relationship to the IP will be summarized.

An AE that occurs more than 30 days after the date of the last dose of IP will not be summarized.

The incidence of common ($\geq 2\%$ of patients) TEAEs and AEs leading to premature discontinuation of IP will be summarized by preferred term and will be sorted by decreasing frequency.

An SAE that occurred between the date of the first dose of the open-label IP and 30 days after the date of the last dose of IP, inclusive, will be considered an on-therapy SAE.

The number and percentage of patients who have on-therapy SAEs will be summarized by preferred term. In addition, the incidence of on-therapy SAEs that led to death will be summarized separately by preferred term.

The incidence of AEs leading to premature discontinuation of IP during the OLTP will be summarized by preferred term and will be sorted by decreasing frequency.

Listings will be presented for all patients with SAEs, patients with AEs leading to discontinuation, and patients who die (if any). All patients with SAEs, including SAEs reported during the screening period and the safety follow-up period, and patients discontinuing because of AEs occurring before the start of IP will be included in these listings.

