9.1.2 Open-label Treatment Period

Approximately 500 patients are planned for enrollment in the OLTP; all patients will receive open-label rapastinel at 450 mg IV (adjunctive to ADT), either weekly or once every 2 weeks, based upon the Investigator's discretion. Patients will skip odd-numbered visits if being treated on a biweekly basis). The once-every-2-weeks schedule can only be initiated on even-numbered visits in order to maintain the appropriate visit schedule. Patients who are on a once-every-2-weeks schedule can be transitioned back to weekly visits at any visit.

Upon completion of the OLTP at Visit 54 (Week 52, ET), patients will enter a 2-week safety follow-up period and will return to the clinic at Visit 55 (Week 54). The maximum duration of the study will be 56 weeks.

The study will be terminated when 100 patients have completed the 52-week OLTP.

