9.7.6.2 Clinical Laboratory Parameters

Descriptive statistics for clinical laboratory values (in SI units) and changes from baseline values at each assessment timepoint will be presented for each clinical laboratory parameter.

In addition, descriptive statistics for values and changes from the baseline values in conventional units at each assessment timepoint will be presented for selected clinical laboratory parameters listed in the Statistical Analysis Plan (SAP).

The number and percentage of patients who have potentially clinically significant (PCS) postbaseline clinical laboratory values will be tabulated. The criteria for PCS laboratory values will be detailed in the SAP. The percentages will be calculated relative to the number of patients with available non-PCS baseline values and at least 1 postbaseline assessment for the OLTP. The numerator will be the total number of patients with available non-PCS baseline values and at least 1 PCS postbaseline value. A supportive tabular display of patients with PCS postbaseline values will be provided, including the PID number, baseline, and all postbaseline (including non-PCS) values. In addition, a tabular display showing all AEs that occurred in patients who had PCS postbaseline clinical laboratory values will be provided.

Shift tables from baseline to end of study for clinical laboratory parameters will be presented for the following categories: low, normal, and high, which are provided by the laboratory vendor.

Patients who meet the potential Hy's Law criteria from the first dose of IP to within 30 days after the last dose of IP will be summarized. Supportive tabular displays will also be provided.

9.7.6.3 *Vital Signs*

Descriptive statistics for vital signs (eg, pulse rate, systolic and diastolic BP, body weight, oral or tympanic temperature, and body weight) and changes from baseline values at each visit and at the end of study will be presented.

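### Section 9.7.6.1 limits treatment-emergent AEs to the open-label period yet sets a 30-day post-dose cut-off, so the tabulation of nonserious follow-up AEs is left in conflict

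*Protocol*

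**What the plan says.** **TEAE and NEAE definitions (protocol 9.7.6.1).**
- Rollover patients: "an AE (classified by preferred term) that occurs during the OLTP will be considered a treatment-emergent adverse event (TEAE"), subject to a comparison with AEs present before the first dose in the lead-in study.
- Those entering de novo have a parallel rule: "an AE (classified by preferred term) that occurs during the OLTP will be considered a TEAE if it was not present". Here the comparison point is the start of open-label dosing, and an AE already there by then counts if it later worsens.
- Newly emergent AEs: "A TEAE occurring during the OLTP will be considered a newly emergent AE (NEAE"), subject to a comparison with the state before the first open-label dose.

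**Cut-offs in the same section.** Two sentences set a limit after dosing: "An AE that occurs more than 30 days after the date of the last dose of IP will not be considered a TEAE" and "An AE that occurs more than 30 days after the date of the last dose of IP will not be summarized".

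**Windows for other safety outputs.** An SAE is on-therapy if it occurred "between the date of the first dose of the open-label IP and 30 days after the date of the last dose of IP" (9.7.6.1). Potential Hy's Law cases are summarized for patients meeting the "criteria from the first dose of IP to within 30 days after the last dose of IP" (9.7.6.2). The vital-sign denominator in 9.7.6.3 names the safety follow-up explicitly.

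**Where the OLTP ends.** Section 9.1.2: "Upon completion of the OLTP at Visit 54 (Week 52, ET), patients will enter a 2-week safety follow-up period". Sections 9.1 and 9.1.3 also treat the follow-up as its own period, and 9.2 gives its purpose as monitoring patients once dosing has stopped.

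**Safety Population.** The synopsis (2.0) asks for at least one dose in this study. Sections 9.7.1.2 and 9.7.6 ask for at least one dose during the OLTP.

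**The concern.** Long-term safety and tolerability is the study's only objective, and the AE tables are its main descriptive output. Under the literal definition, a nonserious AE with onset between Visit 54 and Visit 55 is recorded but is neither a TEAE nor an NEAE. It would be missing from the tables by system organ class and preferred term, by severity, by causality and by frequency. An SAE on the same day would be counted.

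Two programmers could build different tables from this text. One would stop at Visit 54 and the other at 30 days after the last dose, and each could point to a sentence in 9.7.6.1.

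The Safety Population wording raises a smaller question of the same kind. Rollover patients get their first open-label dose at Visit 1, and they can be stopped at Visit 2 on Visit 1 pregnancy, laboratory or ECG results (9.3.1, 9.3.2). If Visit 1 is not part of the OLTP, the two wordings classify such a patient differently.

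**Working it through.** **1. Period lengths.** Sections 9.1 and 9.1.2 give up to 2 weeks of screening, up to 52 weeks of OLTP and 2 weeks of follow-up: 2 + 52 + 2 = 56 weeks. This reproduces the stated maximum duration, so the follow-up lies outside the OLTP.

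**2. Visit calendar.** Visit 53 is Week 51 (9.4.7.2) and Visit 54 is Week 52 (9.1.2), so Visit v falls at Week v − 2. Take Visit 2 as day 0:
- Visit 54, end of OLTP: 52 × 7 = day 364.
- Visit 55, Week 54: 54 × 7 = day 378.

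**3. Last scheduled dose.** Dosing runs from Visit 2 to Visit 53 (9.4.7.2).
- Weekly: Visit 53, day 357.
- Biweekly: odd-numbered visits are skipped (9.1.2, 9.4.7), so Visit 52, Week 50, day 350.

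**4. The 30 days after the last dose, for an on-schedule completer.**

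| | Weekly | Biweekly |
|---|---|---|
| Last dose | day 357 | day 350 |
| Last dose + 30 | day 387 | day 380 |
| Days inside the OLTP | 364 − 357 = 7 | 364 − 350 = 14 |
| Days outside the OLTP | 387 − 364 = 23 (76.7%) | 380 − 364 = 16 (53.3%) |
| of which up to Visit 55 | 378 − 364 = 14 (46.7%) | 14 (46.7%) |
| of which after Visit 55 | 387 − 378 = 9 | 380 − 378 = 2 |

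Up to Visit 55 all AEs go into the eCRF. Afterwards only serious or possibly IP-related AEs do (9.5.2.1.4).

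**5. What the 30-day sentences do under the OLTP limit.** An on-schedule patient leaves the OLTP 7 or 14 days after the last dose. A 30-day cut-off inside the OLTP therefore has an effect only for a patient still in the OLTP more than 30 days after the last dose.

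**6. Early leavers.** Let g be the days from the last dose to the early termination visit, taken as the end of that patient's OLTP. The days outside are 30 − g. The protocol does not give g, so a range is shown:

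| g | 0 | 7 | 14 | 21 | 30 |
|---|---|---|---|---|---|
| Days outside | 30 | 23 | 16 | 9 | 0 |
| Share | 100% | 77% | 53% | 30% | 0% |

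More than half is outside only if g is below 15. With about 500 entrants and termination at 100 completers (9.7.9), up to about 400 patients, (500 − 100)/500 = 80%, may leave before Week 52. The unknown g therefore matters for most of the sample.

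**7. Is the rollover Visit 1 dose in the OLTP?**
- Against: 9.1.1 and 9.4.7.1 place it under screening, the synopsis gives rollover patients a 1-week screening period, and Visits 2 to 54 fill 52 weeks exactly.
- For: 9.4.7.2 names it under the OLTP heading, 9.7.4.1 counts OLTP exposure from the first open-label dose, and 9.7.2 foresees screen failures for de novo patients only.

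The visible text does not settle it.

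**The case against.** The strongest reply is that the authors evidently meant a window to 30 days after the last dose. A sentence excluding AEs after day 30 makes sense only if AEs up to day 30 can count. The NEAE wording, a TEAE that occurs in the OLTP, would be redundant if every TEAE were already confined to that period. This stands as evidence of intent, and it is why the point is an internal conflict and not a deliberate OLTP-only rule. It does not remove the conflict. Both sentences only exclude later AEs and neither extends the definition past the OLTP, whereas 9.7.6.3 names the follow-up where it is meant.

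It can also be said that SAEs and nonserious AEs need not share a window, and that an OLTP-only NEAE table may be intended. Both are fair. A period-specific table is acceptable if it is labelled as one.

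The consequences are limited too. On-therapy SAEs, including fatal ones, are tabulated to day 30. SAEs, deaths and AE discontinuations are listed, including SAEs in the follow-up. All AEs are displayed for patients with potentially clinically significant laboratory, vital-sign or ECG values, or QTc increases above 30 msec (9.7.6.2 to 9.7.6.4). The study has no inferential analysis.

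The SAP, not shown here, may set the working window. That does not excuse the protocol from stating two rules that disagree.

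**Conclusion.** The two rules in 9.7.6.1 cannot both do the work they appear meant to do. On the literal reading, nonserious AEs with onset in the safety follow-up enter no named incidence table. For on-schedule completers this leaves 23 of 30 (weekly) or 16 of 30 (biweekly) post-dose days outside the TEAE window. In both cases 14 of the 30 are days when every AE is still recorded. The figures assume dosing and visits on schedule.

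Three stronger readings should be resisted:
- A reader might infer that most of the post-dose window is lost for the study population as a whole. That is shown only for on-schedule completers; for early leavers it depends on g.
- A reader might infer that TEAE rates are understated by a similar fraction. These are shares of days; the protocol gives no AE counts and no basis for the size of any bias.
- A reader might infer that rollover patients dosed only at Visit 1 vanish from the report. Even if Visit 1 is outside the OLTP, they are counted in the Screened Population on signing consent (9.7.1.1) and so appear in the population counts of 9.7.2.

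The Safety Population wording is a secondary, minor inconsistency. It matters only if the rollover Visit 1 dose lies outside the OLTP, and the number of patients affected is unknown and may be zero.

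**What to change.** - **TEAE window.** In 9.7.6.1, define it as the first open-label dose in RAP-MD-06 through 30 days after the last dose, matching the on-therapy SAE window. Keep the existing pre-dose benchmarks for rollover and de novo patients.
- **NEAE table.** Give it the same window, or keep it OLTP-only and label it as period-specific.
- **Footnote.** State that recording of nonserious AEs is partial after Visit 55, which for on-schedule completers affects the last 9 (weekly) or 2 (biweekly) days of the window.
- **Safety Population.** Use one wording in the synopsis, 9.7.1.2 and 9.7.6: at least one open-label dose in RAP-MD-06, including the rollover Visit 1 dose.

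The cost is wording and table programming; no new data, visits or patients are needed. Reported TEAE percentages may rise slightly because more days are counted.

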- To evaluate the psychotomimetic effects of rapastinel (450 mg IV weekly or once every 2 weeks) as an adjunct to ongoing ADT, as measured by the change from baseline in BPRS+ at all postdose evaluations
- To evaluate the dissociative effects of rapastinel (450 mg IV weekly or once every 2 weeks) as an adjunct to ongoing ADT, as measured by the change from baseline in CADSS at all postdose evaluations

9.0 **INVESTIGATIONAL PLAN**

9.1 **OVERALL STUDY DESIGN AND PLAN: DESCRIPTION**

[figure not shown]
Study RAP-MD-06 is a multicenter, open-label study to evaluate the long-term safety and tolerability of rapastinel as adjunctive therapy to ADT in adult patients with MDD who either completed the RAP-MD-04 Double-blind Treatment Period (DBTP) at Visit 122 (Week 104, ET) or who do not meet criteria to be randomized into the DBTP of RAP-MD-04 and are therefore discontinued from that study. The enrollment of patients who did not participate in RAP-MD-04 (identified as *de novo* enrollment patients) may be considered at some study centers if enrollment of rollover patients does not meet targeted projections and will not be allowed unless specified in an official communication from the Sponsor.

The study will be conducted in the following periods:

- Up to 2-week screening period
- Up to 52-week OLTP
- 2-week safety follow-up period

The study is planned to be terminated when 100 patients have completed the 52-week OLTP. The actual sample size is expected to be larger than 100 patients and some patients will have less than 52 weeks of open-label treatment (as many as 500 patients are expected to enter the OLTP of Study RAP-MD-06).

[Figure 9.1-1](#) provides the study design schematic. The schedule of evaluations is presented in [Section 2.0](#), and detailed descriptions of the procedures conducted at each study visit can be found in [Section 9.5](#).

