9.7.9 Determination of Sample Size

Approximately 500 patients are expected to enter the OLTP. The study will be terminated when 100 patients have completed the 52-week OLTP.

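### Adverse events are summarised only as crude patient percentages with no common time horizon, although up to about 80% of patients will have less than 52 weeks

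*Protocol*

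**What the plan says.** The point concerns the AE tables in protocol sections 9.7.6 and 9.7.6.1.

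- General rule for safety data (9.7.6): "Categorical variables will be summarized by number and percentage of patients". The denominator is the Safety Population, that is, everyone with at least one dose.
- TEAEs: "The number and percentage of patients reporting TEAEs will be tabulated by SOC and preferred term".
- Newly emergent AEs (NEAEs): "The number and percentage of patients reporting NEAEs during the OLTP will be summarized by SOC and preferred term".
- On-therapy SAEs: "The number and percentage of patients who have on-therapy SAEs will be summarized by preferred term".
- Discontinuations: "The incidence of AEs leading to premature discontinuation of IP during the OLTP will be summarized by preferred term". Incidence carries no time unit here, so it falls under the number-and-percentage rule.
- Counting limit: "An AE that occurs more than 30 days after the date of the last dose of IP will not be considered a TEAE". On-therapy SAEs have the same 30-day limit, and NEAEs are counted over the open-label treatment period (OLTP). All these limits depend on the individual patient's own follow-up.

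The amount of follow-up is set elsewhere. Section 9.7.9 states: "The study will be terminated when 100 patients have completed the 52-week OLTP". Section 9.1 says that some patients will have less than 52 weeks, and that "as many as 500 patients are expected to enter the OLTP of Study RAP-MD-06". Section 9.3.4 rules out replacing dropouts. Treatment duration (9.7.4.1) and disposition (9.7.2) are summarised, but neither is linked to the AE counts.

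**The concern.** A crude percentage means the same thing for every patient only if all are observed for the same time. Here a patient cut off at Week 15 and a patient who completes Week 52 count equally in the denominator. The result is an average risk over whatever mix of follow-up accrual, dropout and the stopping date happen to produce.

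Long-term safety and tolerability is the study's sole objective (8.0). Section 9.2 says the 52-week design serves that purpose, and section 7.0 says the study is to support an application for approval. What such a study adds over shorter ones is information on events that appear after months of treatment, and the crude percentage is weakest for those. It also cannot show whether AE risk rises, falls or stays level over the year. Laboratory, vital-sign, ECG, BPRS+ and CADSS data are summarised by visit or timepoint; the AE summary tables have no time dimension.

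**Working it through.** **Share with less than 52 weeks.** Inputs are 500 entrants (9.1, an upper figure) and a stop at 100 completers (9.7.9).

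- 500 entered: 1 - 100/500 = 80%
- 400: 75%; 300: 67%; 200: 50%

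This total combines Sponsor stop and dropout. The protocol does not give the split.

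**Assumptions for the size.** The protocol states no accrual period or dropout rate, so these are assumed: 500 entered uniformly over 26 to 65 weeks, and exponential dropout of 20% to 60% per year. The stop is the time T of the 100th completer, and each patient's follow-up is min(52, dropout time, T - entry time). Every event type is given a true 52-week risk of 10%. The expected crude percentage is the mean, over patients, of the event-time distribution function at the end of each patient's follow-up (500 simulated trials per scenario). The version with the 30-day window adds 30/7 weeks, capped at Week 52.

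Mean follow-up is 30 to 41 weeks. The stop cuts short 23% to 67% of patients and dropout 13% to 57%.

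| Timing of events (true risk 10%) | Crude % | With 30-day window |
|---|---|---|
| Constant rate | 5.9 to 7.9 | 6.5 to 8.4 |
| Only after Week 26 (extreme case) | 3.7 to 6.2 | 4.3 to 7.2 |
| Only Weeks 0-8 | 9.3 to 9.8 | 9.9 to 10.0 |
| Only Weeks 0-12 | 9.0 to 9.8 | 9.6 to 9.9 |

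**Dropout and stop separated (no window).** With dropout alone and a constant rate, the expected crude percentage is a/(a+b) × [1 - exp(-(a+b))], where a = -ln(0.9) = 0.1054 and b = -ln(1 - yearly dropout). At 20% dropout, b = 0.2231, which gives 0.1054/0.3285 × (1 - 0.72) = 9.0%.

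| Yearly dropout | Constant: dropout alone | Stop takes off | Late: dropout alone | Stop takes off |
|---|---|---|---|---|
| 20% | 9.0% | 1.1 to 3.0 points | 8.5% | 2.3 to 4.6 points |
| 40% | 7.9% | 0.7 to 1.9 | 6.8% | 1.4 to 3.1 |
| 60% | 6.6% | 0.3 to 0.7 | 5.1% | 0.5 to 1.4 |

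At 60% dropout, 10 - 6.6 = 3.4 points of the 3.7 to 4.1 point constant-rate shortfall come from dropout.

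**Milder cases.** With 300 entered, the crude figures are 6.5% to 8.3% (constant) and 4.9% to 7.1% (late), and at 60% dropout the stop adds almost nothing. With 500 entered over 13 weeks and no dropout they are 9.2% and 8.5%, or 9.7% and 9.5% with the window.

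**Sensitivity to the ranges.** Entry over 26 to 104 weeks, dropout of 0% to 70%, and a steadily rising hazard (Weibull shape 2) in place of the late-only one give 5.4% to 8.5% (constant) and 4.0% to 7.3% (rising). In the slowest-entry scenarios the stop comes before all 500 have entered.

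**Alternatives under the main assumptions** (entry over 26 and 65 weeks, no window):

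- Kaplan-Meier at Week 52 averages 9.9% to 10.2% for constant, late and early events when dropout is non-informative. The standard deviation is 1.7 to 2.3 points for constant and late events.
- Cumulative incidence with dropout competing averages 9.0-9.1%, 7.9-8.0% and 6.6% (constant) at 20%, 40% and 60% dropout. It removes the stop component only.
- Rates per 100 patient-years are 10.5 to 10.8 for constant events (true 10.5), 6.4 to 8.0 for late events (about 10.2 with full follow-up), and 13.8 to 17.8 for events in the first 8 weeks (about 11.0 with full follow-up).

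**The case against.** The protocol never calls its percentages 52-week risks. They are correct for the population and windows it defines, and the synopsis promises descriptive statistics only. Unequal follow-up is disclosed, exposure and disposition are reported, and Sponsor termination is a listed discontinuation reason. Time-to-event displays for AEs are often left to the SAP, which is not available here. Measuring against 10% also treats dropout as bias. Dropout alone leaves the crude percentage equal to cumulative incidence with dropout competing, and against that target only the stop component counts. Rollover patients, the main source, arrive from RAP-MD-04, which section 9.4.6 describes as lasting 26 weeks to 2 years, so time in this study is not time on drug. The alternatives have weaknesses too: patient-year rates depend on the follow-up mix, and Kaplan-Meier needs non-informative dropout although AE and lack of efficacy are discontinuation reasons.

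Much of this stands and limits the claim. The stop component is small at high dropout, early events are hardly affected, and the time origin for rollover patients needs labelling. Two points do not carry. Section 9.7.6.1 sets out its AE summaries in detail and refers nothing about AEs to the SAP, whereas the laboratory, vital-sign and ECG sections do make such referrals. And reporting mean exposure separately gives a reader at best an approximate overall rate. It gives no risk at a stated time.

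**Conclusion.** The concern holds, as a recommended improvement to the analysis. The crude tables are not wrong, but on their own they do not answer the long-term question. The share with less than 52 weeks, up to about 80%, follows directly from the protocol's figures at its maximum enrolment. The size of the understatement rests on assumed accrual, dropout and event timing. Under the main assumptions it is about 2 to 4 points on a true 10% for constant-rate events, 4 to 6 points in the extreme late-event case, and under 1 point for events in the first 8 weeks. It is also small with fast entry and low dropout. How much of it counts as bias depends on whether the target is risk on continued treatment or risk with dropout as it occurs.

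**What to change.** Keep the crude tables. For NEAEs, on-therapy SAEs and AEs leading to discontinuation, add to section 9.7.6.1:

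1. Patients with a first event per 100 patient-years at risk.
2. Kaplan-Meier or cumulative-incidence estimates at landmark times up to Week 52, with numbers at risk.

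NEAEs already capture onset or worsening in this study, so a separate TEAE version is unnecessary. Specify the following:

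- **Time at risk.** Count from the first RAP-MD-06 dose to the first event or the end of the window that 9.7.6.1 gives for that event type, with the Sponsor stop as administrative censoring. For AEs neither serious nor judged related, end at the final study visit if that is earlier, because section 9.5.2.1.4 does not bring later ones into the eCRF.
- **Target.** Censoring dropout estimates risk on continued treatment. Treating dropout as a competing event estimates risk with dropout as it occurs, and should be used for AEs leading to discontinuation. Note that dropout may be informative.
- **Groups.** Show rollover and *de novo* patients separately, and label rollover results as time since RAP-MD-06 entry.
- **Interpretation.** Base statements on long-term AE risk on item 2, since item 1 alone also depends on the follow-up mix.

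The cost is a few extra descriptive tables from dates already collected, consistent with the rule against inferential analyses. Estimates for constant and late events will look less favourable than the crude percentages. The Week 52 estimate will rest on about 100 patients, with a standard error of about 1.7 to 2.3 points for a 10% risk.
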